## 8.4 REPORTING PROCEDURES

### 8.4.1 ADVERSE EVENT REPORTING

The study coordinator will ask about gastrointestinal health any bleeding events and unusual bruising and fill out the AE forms as events are noted. The DSMB will be informed of all AEs.

### 8.4.2 SERIOUS ADVERSE EVENT REPORTING

The study clinician will complete a SAE Form within the following timelines:

- All deaths and immediately life-threatening events, whether related or unrelated, will be recorded on the SAE Form and submitted to the DSMB within 24 hours of site awareness.
- Other SAEs regardless of relationship, will be submitted to the DSMB within 72 hours of site awareness.

All SAEs will be followed until satisfactory resolution or until the site investigator deems the event to be chronic or the adherence to be stable. Other supporting documentation of the event may be requested by the DSMB and should be provided as soon as possible. The PI will be responsible for notifying FDA of any unexpected fatal or life-threatening suspected adverse reaction as soon as possible but in no case later than 7 calendar days after the sponsor's initial receipt of the information.

#### 8.4.3 UNANTICIPATED PROBLEM REPORTING

None

#### 8.4.4 EVENTS OF SPECIAL INTEREST

None

#### 8.4.5 REPORTING OF PREGNANCY

Although resveratrol is likely to not have any untoward effect during pregnancy either to the mother or the fetus, there is no definitive data on the safety of the supplement during pregnancy. Therefore, pregnancy is considered an exclusion criteria in this study. During enrollment, female participants will be asked about their intention to get pregnant in the next few months. Additionally, female participants of child-bearing age will be asked to practice adequate contraception methods known to prevent pregnancy. They will be asked to notify the study team when they become pregnant and to stop study medication if such an event occurs. A urine pregnancy test will verify potential participants are not pregnant prior to test medication being mailed. A urine pregnancy test will be administered for participants in United States and International participants will self administer urine pregnancy test at the end of first 90 day period of placebo or resveratrol or during the 30 day washout period.

### 8.5 STUDY HALTING RULES

Administration of study agent will be halted study-wide when any of the following occur and are reported to the DSMB:

- three grade 3 AEs
- three grade 1 or grade 2 AEs of the same type
- three grade 1 or grade 2 AEs related to liver function
- one grade 4 or 5 AE

The research coordinator will notify the principal investigators and co-investigator immediately when the the study stopping criteria are met and enrollment screens will stop accepting new study participants. The principal investigator will inform the Data and Safety Monitoring Board (DSMB) members within 24 hours of this occurrence and will provide the DSMB with AE listing reports. The DSMB will convene an ad hoc meeting by teleconference or in writing as soon as possible. The DSMB will provide recommendations for proceeding with the study to the principal investigator. The principal investigator will inform the FDA of the temporary halt and the disposition of the study.

An individual participant will be asked to discontinue study medication if any of the following occur:

- one grade 3, 4, or 5 AE
- three grade 2 AEs
- five grade 1 AEs

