### 8.2 CLASSIFICATION OF AN ADVERSE EVENT

#### 8.2.1 SEVERITY OF EVENT

The AE grading system used is based on NIH National Cancer Institute's Common Terminology Criteria for Adverse Events (CTCAE) version 5.0 at:

[https://ctep.cancer.gov/protocoldevelopment/electronic\\_applications/ctc.htm#ctc\\_50](https://ctep.cancer.gov/protocoldevelopment/electronic_applications/ctc.htm#ctc_50)

Grade refers to the severity of the AE. The CTCAE displays Grades 1 through 5 with unique clinical descriptions of severity for each AE based on this general guideline:

- **Grade 1** Mild; asymptomatic or mild symptoms; clinical or diagnostic observations only; intervention not indicated.
- **Grade 2** Moderate; minimal, local or noninvasive intervention indicated; limiting age-appropriate instrumental ADL\*.

- **Grade 3** Severe or medically significant but not immediately life-threatening; hospitalization or prolongation of hospitalization indicated; disabling; limiting self care ADL\*\*.
- **Grade 4** Life-threatening consequences; urgent intervention indicated.
- **Grade 5** Death related to AE.

*A Semi-colon indicates 'or' within the description of the grade.*

*A single dash (-) indicates a Grade is not available.*

*Not all Grades are appropriate for all AEs. Therefore, some AEs are listed with fewer than five options for Grade selection. Grade 5 (Death) is not appropriate for some AEs and therefore is not an option.*

Adverse Events	Grade of Adverse Event (CTCAE version 5.0)				
	1	2	3	4	5
Kidney Function					
Creatinine increased	>ULN-1.5x ULN	>1.5-3.0x baseline; >1.5-3.0x ULN	>3.0 baseline; >3.0-6.0x ULN	>6.0x ULN	-
Acute Kidney Injury	-	-	Hospitalization indicated	Life-threatening consequences; dialysis indicated	Death
Hyperkalemia (A disorder characterized by laboratory test results that indicate an elevation in the concentration of potassium in the blood; associated with kidney failure or sometimes with the use of diuretic drugs.)	>ULN-5.5 mmol/L	>5.5-6.0 mmol/L	>6.0-7.0 mmol/L; hospitalization indicated	>7.0 mmol/L; life-threatening consequences	Death
Liver Function					
Alanine aminotransferase increased	>ULN-3.0x ULN if baseline was normal; 1.5 - 3.0 x baseline if baseline was abnormal	>3.0-5.0x ULN if baseline was normal; >3.0 - 5.0 x baseline if baseline was abnormal	>5.0-20.0x ULN if baseline was normal; >5.0 - 20.0 x baseline if baseline was abnormal	>20.0x ULN if baseline was normal; >20.0 x baseline if baseline was abnormal	-

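### Read literally, the study-wide halting rule in section 8.5 lets three mixed-grade patterns of same-type or liver events pass, although three grade 1 events of the same kind would halt dosing

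*Combined protocol and SAP*

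**What the plan says.** Section 8.5 opens: "Administration of study agent will be halted study-wide when any of the following occur and are reported to the DSMB". Four triggers follow:

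- three events of grade 3, of whatever type;
- "three grade 1 or grade 2 AEs of the same type";
- "three grade 1 or grade 2 AEs related to liver function";
- a single event of grade 4 or 5.

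No trigger says that higher grades also count, and no sentence adds events from different triggers.

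When a trigger is met, dosing stops and "enrollment screens will stop accepting new study participants". The principal investigator notifies the DSMB within 24 hours with event listings, and the FDA is told of the halt. Section 8.5 adds: "The DSMB will convene an ad hoc meeting by teleconference or in writing as soon as possible".

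The same section has a separate rule for stopping one participant, which begins with "one grade 3, 4, or 5 AE".

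Section 8.2.1 grades ALT, AST, alkaline phosphatase and bilirubin separately. With a normal baseline, ALT is grade 1 from just above the upper limit of normal (ULN) to 3 times ULN, grade 2 above 3 and up to 5 times, and grade 3 at ">5.0-20.0x ULN if baseline was normal".

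**The concern.** A halting rule should not become looser when one event in a set is replaced by a worse one. Read as written, this one does. If one of three grade 1 liver events had been grade 3, it would leave the low-grade count, which falls to two, and the grade 3 count would be only one. Neither trigger is then met.

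A missed trigger loses the automatic dosing halt for the other participants, the stop to enrolment, the 24-hour notice and the obligatory ad hoc DSMB meeting. The other routes to action are discretionary (suspension under section 5.5), carry no deadline (informing the DSMB of all adverse events, section 8.4.1) or are periodic (DSMB meetings under sections 8.6 and 10.4.7.1). Expedited reporting in section 8.4.2 covers serious events, and an asymptomatic grade 3 laboratory rise need not meet the definition in section 8.1.2.

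**Working it through.** The plan states no operating figure for this rule, so there is none to reproduce. The check is an enumeration.

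**Inputs (section 8.5).** Take events of one type, or liver-related events. Let *a* be the number at grade 1-2 and *b* the number at grade 3. Assume no other grade 3 events and no grade 4 or 5 event, since those feed other triggers.

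**Rule as written.** Halt if *a* ≥ 3 or *b* ≥ 3. No halt therefore means *a* ≤ 2 and *b* ≤ 2. Requiring three or more events in total (*a* + *b* ≥ 3) leaves exactly three cases:

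| Grade 1-2 (*a*) | Grade 3 (*b*) | Total | Halt? | Further same-type or liver events until halt |
|---|---|---|---|---|
| 3 | 0 | 3 | yes | - |
| 2 | 1 | 3 | no | 1 if grade 1-2; otherwise 2 |
| 1 | 2 | 3 | no | 1 if grade 3; otherwise 2 |
| 2 | 2 | 4 | no | 1, whatever its grade |
| 0 | 3 | 3 | yes | - |

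The largest total without a halt is 2 + 2 = 4, so the fifth event always halts. Where *b* = 2, one more grade 3 event of any type also halts.

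**Rule with any-grade counting.** Halt if *a* + *b* ≥ 3. The missed patterns fall from three to none. The patterns that newly halt are exactly those three.

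**ALT example (section 8.2.1, normal baselines).**

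- Three participants with ALT just above ULN, all grade 1: *a* = 3, *b* = 0. The study halts.
- Two participants above 5 times ULN (grade 3) and one above 3 times ULN (grade 2): *a* = 1, *b* = 2. The study does not halt.

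The second line holds only if these are the only abnormal liver results. Section 8.5 counts events, not participants, and the liver trigger pools all liver tests. One more grade 3 liver result from the same blood draws makes *b* = 3, and two more grade 1-2 results make *a* = 3. Either would halt the study. A single extra grade 1-2 result gives (2, 2), which still does not.

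**The case against.** The strongest reply is that the gap is narrow and well covered. Much of that stands. Liver tests tend to be abnormal together, so AST, alkaline phosphatase or bilirubin results from the same draws would often close the gap. Any grade 3 event stops the participant concerned. After baseline, blood is drawn only around day 90 or the washout and at day 210, when the affected participant is normally coming off product anyway. For nausea and diarrhea, which section 2.3.1 describes as mild to moderate, the low-grade trigger would usually fire first. These facts limit the severity. They do not put the triggers in order, and stopping one participant does not protect the others. Sparse blood draws also mean that one or two further liver events could be slow to appear.

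A second reply is that the wording is shorthand and higher grades are meant to count. That may be the intention. But where section 8.5 wants higher grades counted, it lists them, as in "one grade 3, 4, or 5 AE". The grade 3 trigger does not need such a list, because one grade 4 or 5 event halts by itself. The two low-grade triggers do need it. The DSMB charter mentioned in section 8.6 might settle the counting, but its content is not in the documents.

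A reader might infer more than the text supports:

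- **That any three grade 1 events halt the study.** They must be of the same type or liver-related.
- **That the DSMB would be unaware of the events.** Section 8.4.1 has it informed of all adverse events.
- **That the participant-level stop needs the same change.** It also counts grades separately, for example "five grade 1 AEs". But sections 5.4.1 and 7.3.3 leave stopping a participant for adverse events to the investigator's judgment, and whether a mix of grade 1 and 2 events should force a stop is a matter for that judgment.

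**Conclusion.** The concern holds as a low-severity flaw in the wording of a safety rule. On a literal reading, exactly three patterns of same-type or liver events, with (grade 1-2, grade 3) counts of (2, 1), (1, 2) and (2, 2), miss an automatic halt that three grade 1 events of the same kind would trigger. The delay is one or two further events.

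This rests on two assumptions: that grades 1 and 2 are pooled within a trigger, as the wording suggests, and that no other grade 3 event and no grade 4 or 5 event has occurred. No probability is attached, because the documents give no basis for how often events in this population would reach grade 3. Nothing here shows bias in the efficacy estimate.

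**What to change.** In section 8.5, change the two low-grade study-wide triggers to *three AEs of the same type, of any grade* and *three AEs related to liver function, of any grade*. Leave the grade 3 trigger, the grade 4 or 5 trigger and the participant-level rule unchanged. State the same counting convention in the DSMB charter.

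The change is a few words and keeps every threshold number the sponsor chose. Its cost is that, in the three patterns above, a temporary study-wide halt pending DSMB advice comes one or two events sooner and may interrupt 90-day treatment periods in progress. The documents give no basis for pricing such an interruption.

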### 8.6 SAFETY OVERSIGHT

Safety oversight will be under the direction of a DSMB composed of individuals with the appropriate expertise, including gastroenterology, infectious diseases and hematology. The DSMB will meet at least semiannually to assess safety and efficacy data on each arm of the study. The DSMB will operate under the rules of an approved charter that will be written and reviewed at the organizational meeting of the DSMB. At this time, each data element that the DSMB needs to assess will be clearly defined. The DSMB will provide its input to PI.

## 9 CLINICAL MONITORING

None

## 10 STATISTICAL CONSIDERATIONS

## 10.1 STATISTICAL AND ANALYTICAL PLANS

The primary outcome (change in pain between baseline and monthly pain average score) will be scored using the the Numeric Pain Rating Scale. Based on prior studies that utilized these scales, a difference of at least 2 units on the 11-point scale are considered to be a reflection of a true change in pain. Median and mean monthly pain will be compared. The pain score on each day of month one will be averaged to obtain the average pain score for month one, and the same will be done for months two and three, and each of the monthly average scores will be compared to baseline. For the secondary outcome measure, baseline HRQoL will be compared to the 30, 60, and 90 day HRQoL scores.

Data from the daily pain logs and the monthly HRQoL assessments will be used to evaluate changes in outcomes within each intervention period stratified by study drug. The analysis will be performed within the framework of the 2x2 crossover study design. Baseline characteristics (demographic and clinical) will be tabulated. Exploratory analyses will be performed to assess differences in outcomes as stated above after further stratification by gender.

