## 10.4 DESCRIPTION OF STATISTICAL METHODS

### 10.4.1 GENERAL APPROACH

Multilevel mixed-effects models will be utilized to assess the data while accounting for the lack of independence of data obtained from multiple time-points while considering the initial (baseline) outcome scores, type of intervention (placebo vs. resveratrol) and the sequence of intervention (placebo first, then resveratrol, or vice versa). This analysis will be performed using STATA (v.14, College Station, TX). Exploratory analyses after stratification by subject's gender will also be performed.

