#### 10.4.8 ADDITIONAL SUB-GROUP ANALYSES

None

---

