#### 10.4.11 EXPLORATORY ANALYSES

None

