### 10.5 SAMPLE SIZE

Although studies haven't quantified pain variability in PSACH, other studies have utilized a pain VAS and have reported standard deviation (SD) of the difference between scores for the same patient of about 10-15 on a 1-100 scale. In addition, previous research by one of the investigators has suggested that a strong placebo effect can be present in studies using the pain VAS at a magnitude of about 20 on a 1-100 scale. Assuming a similar degree of variability in our study population and considering the placebo effect as reported, with a sample size of 30 participants at a Type I error rate of 5%, the minimal detectable difference would be 2.8 units at a SD of 10 and power of 80%, 4.25 at a SD of 15 and power of 80%, 3.3 at a SD of 10 and power of 90%, and 4.9 at a SD of 15 and power of 90%. Considering that there are about 300 potential patients that can be approached through the "Little People of America" support group and the Facebook PSACH group, we should be able to recruit into the study at least half of those highly motivated and invested individuals. We should be able to achieve our sample size of 30 patients for this study, even assuming a considerably high 33% attrition rate. We will screen 60 to enroll 30.

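### Sections 10.1 and 10.4.1 plan exploratory analyses by gender while 10.4.11 says there are none, and separate analyses within each gender would not test whether the treatment effect differs by gender

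*Combined protocol and SAP*

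**What the plan says.** Section 10.1 commits to a gender analysis: "Exploratory analyses will be performed to assess differences in outcomes as stated above after further stratification by gender". Section 10.4.1, after naming mixed-effects models as the general approach, adds: "Exploratory analyses after stratification by subject's gender will also be performed".

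Under "10.4.11 EXPLORATORY ANALYSES" the whole entry is the word None. Under "10.4.8 ADDITIONAL SUB-GROUP ANALYSES" the entry is also None.

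The plan gives no treatment-by-gender interaction, expected gender split, randomisation stratified by gender or rule for interpreting gender results. Section 10.4.9 on multiplicity deals only with repeated measurements.

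**The concern.** There are two problems.

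First, the plan both promises and denies exploratory analyses. Someone reading a later report could not tell from it whether the gender results were prespecified or added after the data were seen.

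Second, the method does not answer the question. Whether resveratrol works differently in men and women is a question about the difference between two effects. Analysing each gender alone estimates the two effects but never compares them. If a p-value is attached to each, one gender can fall below 0.05 and the other above it by chance, with no true difference. Each analysis also uses only part of a small trial. In a rare disease, a mistaken claim that the treatment works in one gender only would be hard to correct later.

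**Working it through.** **Inputs from the documents**

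- Size and error rate, section 10.5: "with a sample size of 30 participants at a Type I error rate of 5" per cent. Sidedness is not stated; I assume two-sided.
- Variability, section 10.5: "standard deviation (SD) of the difference between scores for the same patient of about 10-15 on a 1-100 scale", which is 1.0 to 1.5 on the 0-10 scale.
- Section 10.5 effects: "the minimal detectable difference would be 2.8 units at a SD of 10 and power of 80%, 4.25 at a SD of 15" at 80% power, and 3.3 (SD 10) or 4.9 (SD 15) at 90%.
- Other effects: 2.8 points on 0-10 (section 10.2) and 2 points as a true change (section 10.1).

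The gender split is not in the documents. I assume 15/15 to 20/10.

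**Step 1. The plan's own figures.** The paired detectable difference is (1.960 + z_power) × SD / √n. For n = 30, SD 10 and 80% power: 2.802 × 10 / 5.477 = 5.1, against the stated 2.8. The four values at n = 30 are 5.1, 7.7, 5.9 and 8.9, against the stated 2.8, 4.25, 3.3 and 4.9. At n = 100 the formula gives 2.80, 4.20, 3.24 and 4.86, close to the stated set. Section 10.6.1 does speak of enrolling one hundred people. So the power of the trial at 30 is unsettled, and the calculation has to be run under several effects.

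**Step 2. Power within each gender.** With p1 and p2 the powers of a paired t-test in each gender (noncentral t) for the same true effect:

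P(exactly one significant) = p1(1 − p2) + p2(1 − p1)

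If all 30 together have 80% power, the effect is 0.529 SD, or 5.3 to 7.9 on the 1-100 scale.

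- 15/15: p1 = p2 = 0.480. Exactly one: 2 × 0.480 × 0.520 = 0.499. Both: 0.230. Neither: 0.271.
- 20/10: p1 = 0.613, p2 = 0.322. Exactly one: 0.613 × 0.678 + 0.322 × 0.387 = 0.540.

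Simulation of 400,000 trials at 15/15 gave 49.9%.

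**Step 3. The same calculation with the documents' own effects at n = 30**

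| Effect and SD | Overall power | Exactly one, 15/15 | Exactly one, 20/10 |
|---|---|---|---|
| 2.8, SD 10 (1-100 scale) | 32% | 29% | 29% |
| 4.25, SD 15 | 32% | 29% | 30% |
| 3.3, SD 10 | 42% | 35% | 35% |
| 4.9, SD 15 | 41% | 34% | 35% |
| 2 points on 0-10, SD 1.0 to 1.5 | about 100% | 0 to 0.5% | 0 to 4% |
| 2.8 points on 0-10, SD 1.0 to 1.5 | about 100% | about 0% | at most 0.1% |

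In the first four rows the commonest outcome is neither gender significant (60 to 68%). In the last two it is both.

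**Step 4. No effect at all.** P(at least one false positive in two independent tests) = 1 − 0.95² = 0.0975, or 9.8%. A single interaction test keeps this at about 5% (4.9% in the simulation, which had a common effect).

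**Step 5. What an interaction could detect.** This compares the mean within-patient difference between genders. At 15 v 15 the standard error is SD × √(1/15 + 1/15) = 0.365 SD. The normal approximation gives 2.802 × 0.365 = 1.02 SD for 80% power; the t-distribution gives 1.06 SD. That is 10.6 to 15.9 on the 1-100 scale, twice the 0.529 SD main effect.

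**The case against.** The strongest reply is that the plan states no decision rule. It says outcomes will be looked at after stratification, and labels this exploratory. It does not mention p-values within gender, a threshold or a gender-specific claim, and stratified estimates with intervals would fit its wording. This stands. The probabilities above describe what happens if results are read through separate tests, which the plan neither proposes nor rules out.

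A reader might also infer that a split result occurs about half the time whenever the effect is identical, or that it is the most likely pattern under a common effect. The documents do not support either as a general statement. At 15/15, a chance of 45% or more needs overall power of about 63 to 93%, and no effect stated in the plan gives that at 30 participants. If 100 were enrolled, the 2.8 effect at SD 10 would return to about half: with 50 per gender the power is 0.4925 each, and 2 × 0.4925 × 0.5075 = 0.50. But the enrolment figure is itself in conflict.

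It can fairly be said, too, that 10.4.8 is headed Additional, so its None may mean none beyond the gender analyses already named. Only 10.4.11 clashes clearly.

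Finally, an interaction estimate from 30 people will be imprecise. That is true, but it shows the uncertainty that two separate analyses hide.

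**Conclusion.** The point holds, and it is minor. The conflict between 10.1 and 10.4.1 on one side and 10.4.11 on the other is in the current text. Section 10.4.8 should be aligned but is not a clear contradiction. Separate analyses by gender do not test for a difference in effect.

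The chance of a misleading split depends on the true effect: about 50 to 54% if 30 participants have 80% power overall, about 29 to 35% under the section 10.5 effects, and about 0 to 4% under the 2 to 2.8 point effects. All of these assume 30 analysed participants, a paired two-sided 5% test, an identical effect and variability in both genders, and a split between 15/15 and 20/10. The primary comparison and its error rate are not touched.

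**What to change.** In 10.1 and 10.4.1, replace the stratified analyses with one treatment-by-gender interaction term in the planned mixed model. Report the difference in effect between genders with its 95% confidence interval, and the two gender-specific estimates with intervals from the same model. Keep the exploratory label and give no p-values within gender. In 10.4.11, and for consistency in 10.4.8, name this analysis in place of None.

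The cost is a few lines of wording, with no extra data or participants. The small downside is imprecision: with about 1.06 SD detectable at 15 v 15, the text should say that a non-significant interaction is not evidence of no difference. Because 10.4.2 allows ranked values or a zero-inflated negative binomial model, the text should also say on which scale the interaction is reported if either is used.
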